Study 2: Effect of Dapagliflozin on EGP With Glucose Clamp: EGP will be measured with 3-³H-glucose infusion as described in Study 1 above. The 3-³H-glucose infusion will be started at 6 AM to measure the basal rate of EGP. After a 3 hour tracer equilibration period (at 9 AM) subjects will receive dapagliflozin (10 mg) or placebo, and the plasma glucose conc will be measured every 5 minutes for 5 hours (from 9AM to 2 PM). A variable infusion of 20% dextrose will be adjusted to clamp the plasma glucose conc at the fasting level (+5%) until the end of the study (2 PM). Blood samples will be drawn every 10-20 minutes for 5 hours (2 PM) for the measurement of plasma glucose, insulin, C-peptide, glucagon, cortisol, catecholamine concentrations and [3-³H]-glucose specific activity. Urine will be collected from 6 to 9 AM and from 9 AM to 2 PM. Urinary volume and glucose concentration will be measured and the rate of urinary glucose excretion quantitated. The study will end at 2 PM and subjects will be allowed to return home. Basic metabolic panel will be performed during the study to monitor renal function.

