Study 3: Effect of Dapagliflozin on EGP with Pancreatic Clamp: In this study, EGP will be measured as described in Study 1 above and plasma insulin and glucagon concentrations will be clamped at the basal level using the pancreatic clamp technique, while the plasma glucose concentration will be allowed to decrease spontaneously after dapagliflozin and placebo administration. Somatostatin (750 µg/h) infusion will be started at 5:45 AM (15 minutes before the start of [3-³H]-glucose infusion [6 AM]) along with basal infusions of glucagon (0.3 ng/kg.min) and insulin (0.1 mU/kg.min) to replace basal plasma glucagon and insulin concentrations. The somatostatin, glucagon and insulin infusions will be continued for the entire duration of the study (until 2 PM). At 6 AM a prime (0.4 uCi x FPG) – continuous (0.4 uCi/min) infusion of [3-³H]-glucose will be started and continued to 2 PM. At 9AM, subjects will ingest dapagliflozin (10 mg) or placebo (2:1 randomization ratio) and blood samples will be drawn at -30, -20, -10, 5 and 0 minutes before and every 10-20 minutes after drug administration (until 2 PM) for the measurement of plasma glucose, insulin, C-peptide, glucagon, cortisol, catecholamine concentrations, and plasma [3-³H]-glucose specific activity. Urine will be collected from 6 to 9 AM and from 9 AM to 2 PM. Urinary volume and glucose concentration will be measured and the rate of urinary glucose excretion will be calculated. The study will end at 2 PM. Basic metabolic panel will be performed during the study to monitor renal function.

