Data Analysis Plan: Data Analysis and Statistical Methods: Under steady-state postabsorptive conditions, the basal rate of endogenous glucose appearance ($R_a = bEGP$) equals the 3-³H-glucose infusion rate divided by steady state plasma tritiated glucose specific activity. After drug administration, non-steady conditions for 3-³H-glucose specific activity prevail and the rate of whole body glucose appearance (R_a) is calculated from Steele's equation. During the glucose clamp study, the rate of EGP after drug administration equals R_a minus glucose infusion rate, while, during the pancreatic clamp, $R_a = EGP$ since no cold glucose is infused. The difference in EGP during the last hour of the study (240-300 minute) between subjects receiving dapagliflozin and subjects receiving placebo represents the increase in EGP caused by dapagliflozin (glucosuria-stimulated increase in EGP). The glucosuria-stimulated increase in EGP will be compared among the three studies with ANOVA. Post hoc testing will be performed with a Bonferroni correction for multiple comparisons. The difference in glucosuria-stimulated increase in EGP between study 2 and study 1 represents the contribution

of the decrease in plasma glucose conc to the increase in EGP, while the difference between study 3 and study 1 represents the contribution of change in islet hormones (insulin/glucagon) to the increase in EGP.

Item 7 Risks Section:

Complete the following table to describe the risks of all **research procedures** listed in Step 2, Institutional Form (items 28-34). *Do not list risks of Routine care procedures here.*

N/A, Risks are described in the informed consent document – do not complete this table.

Research procedures	Risks
example: 
• History and physical• Questionnaire• Laboratory tests	List the reasonably expected risks under the following categories as appropriate:
Add or delete rows as needed	

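### Study 3 leaves glucose free, so a larger fall there could make the Study 3 versus Study 1 contrast understate the hormone contribution, by an unknown amount that may be zero

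*Combined protocol and SAP*

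**What the plan says.** All three measurement days are described in Item 6.

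- **Study 1:** neither glucose nor hormones are controlled after dapagliflozin or placebo.
- **Study 2:** glucose is controlled and the hormones are free: "A variable infusion of 20% dextrose will be adjusted to clamp the plasma glucose conc at the fasting level".
- **Study 3:** the hormones are controlled: "plasma insulin and glucagon concentrations will be clamped at the basal level using the pancreatic clamp technique". Glucose is not: "while the plasma glucose concentration will be allowed to decrease spontaneously after dapagliflozin and placebo administration". The data analysis plan confirms that rate of appearance equals EGP on this day "since no cold glucose is infused".

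The outcome on each day is "The difference in EGP during the last hour of the study (240-300 minute) between subjects receiving dapagliflozin and subjects receiving placebo". Two contrasts are then interpreted. For glucose: "The difference in glucosuria-stimulated increase in EGP between study 2 and study 1 represents the contribution", where the contributor named is the fall in plasma glucose. For hormones: "the difference between study 3 and study 1 represents the contribution of change in islet hormones (insulin/glucagon) to the increase in EGP".

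Plasma glucose is sampled every 10-20 minutes after dosing in Studies 1 and 3. The plan has no step that compares, matches or adjusts for the size of the glucose fall on those two days.

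**The concern.** The plan treats the glucose fall and the hormone change as two separate contributors to the EGP rise. For Study 3 versus Study 1 to isolate the hormones, the other contributor must be the same on both days. It is left free on both, and free does not mean equal.

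If hormones drive part of the EGP rise, fixing them removes that part. Urinary glucose loss continues, so the net glucose deficit is larger and glucose falls further in Study 3. If a falling glucose raises EGP by some route that does not pass through insulin or glucagon, the extra fall raises EGP in Study 3 and shrinks the contrast. A small Study 3 versus Study 1 difference could then be reported as a small hormonal role when part of that role had been masked. The hormonal role is the trial's stated purpose (Item 2).

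**Working it through.** The plan gives no effect size, SD or expected contrast, so there is no figure of its own to reproduce. The check is a mass balance on the dapagliflozin-minus-placebo difference.

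**Inputs**
- Offset *o*: the share of urinary glucose loss replaced by the EGP rise in type 2 diabetes, about 0.5 (Item 3, Background).
- Study 1 EGP rise, scaled to 1: *h* + *g* + *r* = 1. Here *h* is the hormone share, *g* the part of the glucose-fall effect that bypasses the islet hormones, and *r* the remainder. The documents give none of these; all values used are assumptions.
- The glucose fall *D* is taken as proportional to urinary loss minus EGP rise.

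**Steps**
1. Urinary loss is 1/*o* = 2, so the Study 1 deficit is D1 = 2 − 1 = 1.
2. In Study 3 the hormone share is removed and the non-islet share scales with the fall: E3 = *g* × D3/D1 + *r*, with D3 = 2 − E3.
3. Solving, E3 = (2*g* + *r*)/(1 + *g*) = 1 − *h*/(1 + *g*).
4. The observed contrast is 1 − E3 = *h*/(1 + *g*), against a true value of *h*. The hidden share is *g*/(1 + *g*), whatever *h* is.
5. The ratio of falls is D3/D1 = 1 + *h*/(1 + *g*).

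**Results with *o* = 0.5 and *h* = 0.5**

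| *g* (assumed) | Study 3 fall / Study 1 fall | Observed contrast (true 0.50) | Hidden share |
|---|---|---|---|
| 0 | 1.50 | 0.50 | 0% |
| 0.10 | 1.45 | 0.45 | 9% |
| 0.25 | 1.40 | 0.40 | 20% |
| 0.50 | 1.33 | 0.33 | 33% |

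**Sensitivity**
- For other offsets the hidden share is *gc*/(1 + *gc*), with *c* = *o*/(1 − *o*). At *g* = 0.25 it is 14% for *o* = 0.4 (0.167/1.167) and 27% for *o* = 0.6 (0.375/1.375).
- A five-hour simulation averaged over 240-300 minutes gave the same hidden shares, with or without damping of the fall through lower disposal and urinary loss.
- Suppose the free insulin fall in Study 1 also lowers glucose disposal, by an assumed 10% of urinary loss (0.2). Then D1 = 0.8, and with *h* = 0.5 the hidden share is 33% at *g* = 0.25 and 54% at *g* = 0.50. It remains 0% at *g* = 0.
- If the Study 3 fall equalled the Study 1 fall, the contrast would equal *h* and nothing would be hidden.

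**The case against.** The strongest objection is that Study 2 does not show that a glucose fall could act in Study 3. The islets are free in Study 2, so Study 2 versus Study 1 captures the total effect of the fall, including whatever runs through glucagon and insulin. Those hormones are fixed in Study 3, so only a non-islet effect can refill the gap. No part of the documents asserts one, and the Background points towards glucagon. This stands: if the non-islet effect is zero, nothing is hidden. A reader might infer that the plan's reason for Study 2 proves the bias, but it does not.

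Second, preventing the hormone change and letting glucose respond is a legitimate total effect, and the raw contrast estimates it. This also stands. However, the analysis plan presents hormones and glucose as separate contributions, and for that reading the falls need to be comparable.

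Third, a reader might infer that glucose must fall further in Study 3. That is conditional: the clamp has to block part of the EGP rise, and the fixed infusions have to hold the hormones near basal. Drift from imperfect infusions that is common to both arms is removed by the placebo subtraction, but only the data can show which day had the larger drug-induced fall.

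**Conclusion.** The point holds as a conditional underestimate. The hormone reading of Study 3 versus Study 1 requires equal drug-induced glucose falls. The plan neither ensures nor checks this, and under the trial's own hypothesis a larger fall in Study 3 is expected. The contrast is then too small to the extent that a glucose fall raises EGP by a non-islet route. The size is unknown and may be zero. The 0% to 33% in the table is an illustration in which only the 50% offset comes from the documents.

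Two stronger readings are not supported.

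- **A definite, large bias.** A kinetic model with an assumed EGP sensitivity *s* of 0.005-0.02 mg/kg/min per mg/dl and clearance *Cl* of 0.02-0.03 dl/kg/min gives a plateau hidden share *s*/(*s* + *Cl*) from 0.005/0.035 = 14% to 0.02/0.04 = 50%. Neither input is in the documents, and the range leaves out *s* = 0. With a 50% offset (of urinary loss at the starting glucose), *g* = *s*/*Cl* at plateau, so the top end means *g* = 1 and leaves nothing for hormones to contribute.
- **A bias that is worst when hormones matter most.** Since *g* cannot exceed 1 − *h*, a hormone share of 0.8 limits *g* to 0.2 and the hidden share, in the basic model, to 0.2/1.2 = 17%. A dominant hormonal role would still show as a large contrast.

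**What to change.** Add two items to the data analysis plan in Item 6, before analysis:

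1. **A glucose comparison.** For Studies 1 and 3, report the dapagliflozin-minus-placebo change in plasma glucose from pre-dose to the last hour (240-300 minutes). Give the within-subject Study 3 versus Study 1 difference with its confidence interval, beside the EGP contrast.
2. **An interpretation rule.** If glucose falls more in Study 3, the raw Study 1 minus Study 3 EGP difference is a lower bound on the hormone contribution at matched glucose, and a small difference may not be read as a small hormonal role. If glucose falls less in Study 3, the direction reverses. The rule assumes that a glucose fall does not lower EGP by a non-islet route.

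A bracketed estimate could be shown as an exploratory sensitivity analysis only. It adds *s* times the extra glucose fall to the raw contrast, with *s* from 0 to the Study 1 minus Study 2 EGP difference divided by the Study 1 glucose fall. The text should say that the upper end includes islet-mediated effects, so it can over-correct, and that the ratio is imprecise with 10 placebo subjects.

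The cost is one table and a few sentences, with no new visits, samples or subjects and no change to the clamp procedure. The downside is that the hormone contribution may have to be reported as a bound rather than a single figure.

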COVER PAGE FOR PROTOCOL AND STATISTICAL ANALYSIS PLAN

Official Study Title: SGLT2 Inhibition and Stimulation of Endogenous Glucose Production:
Protocol 2

NCT number: NCT02592421

IRB Approval Date: 09/06/2017

Protocol Template Form

Item 1 UTHSCSA Tracking Number	HSC20150668H
-----------------------------------	--------------

Item 2 Abstract / Project Summary	
Provide a succinct and accurate description of the proposed research. State the purpose/aims. Describe concisely the research design and methods for achieving the stated goals. This section should be understandable to all members of the IRB, scientific and non-scientific.
 
DO NOT EXCEED THE SPACE PROVIDED.

------------------------------------------	---------------------------------------------------------------------------------------------------------------------------------------------------------------------------------------------------------------------------------------------------------------------------------------------------------------------------------------------------------------------

Purpose/Objectives: We will determine the role of pancreatic hormones (increase in plasma glucagon and decrease in plasma insulin concentration) in the stimulation of EGP following SGLT2 inhibition.

Research Design/Plan: After screening, eligible subjects will receive three 5-hour measurements of EGP with administration of study drug after a 3-hour tracer equilibration period. HGP will be measured for 5 hours after drug administration to allow sufficient time for a significant increase in HGP above baseline after dapagliflozin administration (10). In study 1, HGP will be measured for 5 hours after dapagliflozin (10 mg) or placebo administration. Study 2 will be performed under glucose clamp conditions (i.e. maintaining the plasma glucose concentration stable at each subject's fasting level), and Study 3 will be performed under pancreatic clamp conditions (maintaining the plasma glucagon and insulin concentrations constant at the basal level). Subjects will be randomized in a 2:1 ratio; 20 subjects will receive dapagliflozin and 10 subjects will receive placebo. Each study will be performed on a separate day, after a 10-12 hour overnight fast within 1-2 week period.

Methods: Screening visit; Study 1 EGP, Study 2 EGP with Glucose Clamp, Study 3 EGP Pancreatic Clamp

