EGP measurement with 3-3H-glucose with Pancreatic Clamp	
 ○ Blood draws and cath placement: 
 ○ fainting, pain, bruising, swelling, bleeding, anemia or rarely infection where the needle is inserted. ○ In rare cases the area where the needle is inserted can also become infected or nerves may be damaged, inducing long-lasting abnormal sensations (paresthesia), impaired sensation of touch and persistent pain ○ Some people may experience mild pain from the catheter. On rare occasions, inflammation of the vein may occur or bruising or black and blueness may occur over the puncture site. Such complications occur in less than 1% of individuals and, if they occur, they usually go away on their own in 2-3 days and are helped by using hot packs. ○ Radiation exposure 
There is no known minimum level of radiation exposure that is recognized as being totally free of the risk of causing genetic defects (abnormal cells) or cancer. However, the probability of harm from such risk associated with the amount of radiation exposure received from this study is considered to be low when compared to other everyday risks each member of the general public receives per year, depending on the
 ○ Substances Infusion: 
Insulin: Insulin is a hormone that naturally is abundant in your body. The only potential side effect known for insulin is hypoglycemia. We will measure your blood sugar every half to 2 hours during the insulin infusion to prevent hypoglycemia from happening. From our previous experience this side effect never happened during our past studies. If you do develop low blood sugar, we can easily make your blood sugar return to normal by giving you glucose.
 
Glucose, glucagon and somatostatin hormones: these substances are abundant in the body and there is no known side effect for their infusion in the amounts we will be giving you.
 ○ Heated box: 
During visits 2, 3, and 4 , the hand is placed in a transparent plastic thermo regulated box heated to 70°C (158°F). Rarely, the hand may suffer a burn or blister. Please tell us if your hand is too hot or feels uncomfortable while in the heated box, in which case your hand will be removed from the box but the test will be continued.
 ○ Dapagliflozin: 
 ○ Likely and not serious: ○ These risks are expected to occur in more than 20 out of 100 subjects: Nausea ○ ○ Less likely and not serious: ○ These risks are expected to occur in 5-20 subjects or less out of 100 subjects: vomiting, diarrhea, constipation, GI upset, dizziness, fatigue, headache, runny nose, and in less than 4 out of 100 individuals low blood sugar (also called Hypoglycemia), urinary tract (about 1%) and genital infections (about 4%) ○ ○ Rare and serious: loss of consciousness (or syncopy), decrease in blood pressure (less than 1%), and bladder cancer (less than 0.2%). ○ ○ Safety considerations for dapagliflozin and other SGLT2 inhibitors: ○ Dapagliflozin – is a sodium-glucose cotransporter 2 (SGLT2) inhibitor indicated as an adjunct to diet and exercise to improve glycemic control in adults with type 2 diabetes mellitus and is a member of a class of antidiabetic medications that work by increasing the glucose excretion in the urine. Dapagliflozin (FARXIGA) has been approved by the U.S. FDA. Side effects reported with dapagliflozin will be summarized below based upon http://www1astrazeneca-us.com/pi/pi_farxiga.pdf ○ ○ Hypotension ○ Dapagliflozin may cause intravascular volume contraction. Symptomatic hypotension can occur after initiating dapagliflozin particularly in patients with impaired renal function (eGFR less than 60 ±5 mL/min/1.73 m²), elderly patients, or patients on loop diuretics. Subjects with eGFR less than 60 ±5 mL/min/1.73 m² will not be allowed in the study. Signs and symptoms of hypotension after initiating therapy will be monitored. If a participant experiences any of these, the dapagliflozin will be stopped and the participant will be discontinued from the study. ○ Renal Function ○ A small decrease in kidney function (eGFR) and increase in serum creatinine has been observed when dapagliflozin is initially started. The eGFR gradually returns toward normal while the drug is continued and returns to normal if drug is stopped. If the eGFR drops below 60 or if the serum creatinine rises by ≥3.0 mg/dl the dapagliflozin will be stopped and the participant will be discontinued from the study. Sudden kidney injury (acute kidney injury) has happened to people taking dapagliflozin. Talk to your doctor right away if you: 
 ○ reduce the amount of food or liquid you drink for example, if you are sick or cannot eat or ○ you start to lose liquids from your body for example, from vomiting, diarrhea or being in the sun too long. Seek medical attention immediately if you experience signs and symptoms while taking these medicines such as:

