
- ○ Decreased urine
 - ○ Swelling in your legs or feet
- Hypoglycemia
- Hypoglycemia (low blood sugar) – can occur with any antidiabetic medication. In studies of dapagliflozin, the frequency of hypoglycemia was less than 5% and similar to that in the placebo group. Subjects will be told to call the investigator if symptoms (sweating, rapid thumping heartbeat, mental confusion) of hypoglycemia occur and to drink a glass of orange juice with a packet of sugar. Any subjects with hypoglycemia will be evaluated for potential causes. If the hypoglycemia recurs, the subject will be discontinued from the study.
- Serious urinary tract infections
- Serious urinary tract infections that may lead to hospitalization have happened in people who are taking dapagliflozin. Tell your doctor if you have any signs or symptoms of a urinary tract infection such as a burning feeling when passing urine, a need to urinate often, the need to urinate right away, pain in the lower part of your stomach (pelvis), or blood in the urine. Sometimes people also may have a fever, back pain, nausea or vomiting. You should seek medical attention and contact your study doctor immediately if you experience any of these symptoms.
- Genital Mycotic Infections
- Vulvovaginitis, balanitis and related genital infections were reported in 4.8% and 0.9% of subjects who received dapagliflozin 10 mg and placebo, respectively. Most infections were mild to moderate, and subjects responded to an initial course of standard treatment and rarely resulted in discontinuation from dapagliflozin treatment. These infections were more frequent in females (6.9% and 1.5% for dapagliflozin and placebo, respectively), and subjects with a prior history were more likely to have a recurrent infection.
- If you experience an genital infection call the study doctor. You will be treated with a local antifungal cream or oral antibiotic therapy. .
- Volume depletion
- Dapagliflozin increases the amount of salt and water that is excreted in the urine. Reactions related to volume depletion (including dehydration, hypovolemia, orthostatic hypotension, or hypotension) were reported in 0.8% and 0.4% of subjects who received dapagliflozin 10 mg and placebo, respectively; serious reactions occurred in < 0.2% of subjects balanced between dapagliflozin 10 mg and placebo.
- Call the investigator if you experience symptoms of volume depletion.
- Malignancies

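### Does the Study 3 rule EGP = Ra fail if a subject is given glucose for low blood sugar?

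*Combined protocol and SAP*

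**What the plan says.** Item 6, Data Analysis and Statistical Methods, describes Ra as appearance of glucose in the whole body and derives EGP from it separately for each clamp. For the glucose clamp (Study 2), "the rate of EGP after drug administration equals R_a minus glucose infusion rate". For the pancreatic clamp (Study 3), EGP is Ra itself, "since no cold glucose is infused". The outcome is EGP at 240-300 minutes, dapagliflozin against placebo. The Study 3 effect compared with the Study 1 effect is read as the islet-hormone contribution.

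Item 6, Study 3, lists infusions of somatostatin, glucagon, insulin and labelled glucose but no dextrose. Plasma glucose is not held: "while the plasma glucose concentration will be allowed to decrease spontaneously after dapagliflozin and placebo administration".

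Item 7, pancreatic-clamp row, Substances Infusion, says of the insulin infusion: "If you do develop low blood sugar, we can easily make your blood sugar return to normal by giving you glucose". It adds: "From our previous experience this side effect never happened during our past studies". It then lists "Glucose, glucagon and somatostatin hormones: these substances are abundant in the body and there is no known side effect for their infusion". Under Hypoglycemia, the same row says of dapagliflozin studies in general that "the frequency of hypoglycemia was less than 5% and similar to that in the placebo group".

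On numbers, Item 2 states that "20 subjects will receive dapagliflozin and 10 subjects will receive placebo".

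**The concern.** Ra contains every source of unlabelled glucose. If a Study 3 subject received glucose and it entered the circulation during the last hour, Ra would be EGP plus that glucose, and setting EGP equal to Ra would overstate EGP by the added amount. The only subtraction in the plan is tied to Study 2. Nothing says whether an affected Study 3 value is corrected, dropped or kept.

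The contrast at stake is the main one. Glucose given to a dapagliflozin subject would inflate the Study 3 drug effect and make the islet-hormone contribution look smaller. Glucose given to a placebo subject would do the opposite. With 10 placebo subjects, one case carries a tenth of the arm mean.

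**Working it through.** The plan gives no effect size, standard deviation or power for this outcome, so there is no figure of its own to reproduce. The check has two parts.

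**Reading the sections together**

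- The Study 3 identity rests on a stated premise, that no unlabelled glucose is given. Within that premise it is exact. It does not tell the analyst to go on equating EGP with Ra once the premise has failed.
- The general relation is EGP = Ra - rate of exogenous glucose. Study 2 uses it with a non-zero rate. Study 3 is the same relation with the rate at zero.
- Item 6 describes the planned procedure. The Item 7 sentence is a safety contingency, written to the participant in consent style. A planned glucose-free day and a provision for an unplanned event do not contradict each other.
- The listing of glucose among the infused substances is not evidence of unlabelled glucose, because labelled glucose is itself infused in Study 3. Only the sentence about correcting low blood sugar supports the concern.

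**Size if the event occurred**

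Assumptions, none of them in the documents: 10-25 g, all entering the circulation within 240-300 minutes, in a 90 kg subject.

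Overstatement in that subject = grams × 1000 / (kg × 60 min)

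- 10 g: 10,000 / 5,400 = 1.85 mg/kg/min
- 25 g: 25,000 / 5,400 = 4.63 mg/kg/min

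Shift in the Study 3 drug effect = overstatement / number in the arm

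- One of 20 on dapagliflozin: 1.85/20 = +0.09 to 4.63/20 = +0.23
- One of 10 on placebo: -1.85/10 = -0.19 to -4.63/10 = -0.46

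Range over body weight, using the eligible BMI of 25-45 at an assumed height of 1.70 m: 25 × 1.70² = 72.25 kg and 45 × 1.70² = 130.05 kg.

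- 10 g at 130.05 kg: 10,000 / 7,803 = 1.28, so +0.06 (dapagliflozin) or -0.13 (placebo)
- 25 g at 72.25 kg: 25,000 / 4,335 = 5.77, so +0.29 (dapagliflozin) or -0.58 (placebo)

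Glucose cleared before 240 minutes adds little or nothing.

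**Expected bias**

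With per-subject chance p in both arms and the same overstatement x, the expected bias is 20px/20 - 10px/10 = 0. With unequal chances it is x × (difference in chance). For example, 5% on dapagliflozin and 0% on placebo gives 0.05 × 1.85 = 0.09 to 0.05 × 4.63 = 0.23.

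**Chance of at least one case among 30**, 1 - (1 - p)^30, for an assumed p:

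| p | Chance |
|---|---|
| 0 | 0% |
| 0.5% | 14% |
| 1% | 26% |
| 2% | 46% |
| 5% | 79% |

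The documents give no value of p for the event that matters, which is glucose entering during the last hour of a pancreatic clamp. The 5% row borrows the ceiling of a figure for any hypoglycaemia in general dapagliflozin studies, so it is an outer bound and not a forecast. The site's own past experience is none.

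**The case for a change.** The best case for a change has four parts.

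1. The event is conceivable. Insulin runs at a fixed rate to the end of the day, glucose is left to fall, and subjects on a sulfonylurea are eligible.
2. The outcome window is the last hour, where late-given glucose would land.
3. Subtraction works only for an infusion at a known rate. For oral or bolus glucose the entry rate is unknown, so someone must decide whether to drop the value, and deciding after seeing the arm invites bias.
4. The zero expected bias needs equal frequency and amount in the two arms, and the similar-to-placebo figure does not come from clamp studies. A general formula would cost a sentence.

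Parts 2 and 4 stand as statements of fact. Part 3 stands in that the plan leaves a judgement open. It is a narrow one, however. A value contaminated by glucose of unknown entry rate is invalid as a measurement, for a reason that does not depend on the arm or the result, and a competent analyst would set it aside and say so. Part 1 is weakened by the documents' own account: subjects have type 2 diabetes, the background section describes the EGP rise in such patients while glucose is still in the hyperglycaemic range, hormones are replaced at basal level, and the site reports no earlier occurrence.

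**Conclusion.** The concern does not call for a change. No rule covers a Study 3 subject given glucose, but this is missing detail about an unlikely event and not a wrong formula. The planned analysis is sound as written. The plan already subtracts exogenous glucose where it expects any, and an analyst meeting an affected subject would extend that subtraction to a known infusion rate or set the value aside.

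The size cannot be derived from the documents. Under the assumed grams, timing and weights, one affected subject would shift the Study 3 effect by +0.06 to +0.29 mg/kg/min (dapagliflozin) or -0.13 to -0.58 (placebo). Expected bias is zero if frequency and amount are equal across arms, and the realised shift is zero if no one is affected. Without a stated standard deviation or expected effect, nothing in the plan shows whether even the larger figures would alter a conclusion. This takes no view on when or how glucose should be given.
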